671 trapping, six minute walk distance (6MWD), and health-related quality of life. Longitudinal
672 analyses will be performed with quantitative imaging phenotypes from the Phase 1, 2, and 3
673 visits. Key predictor variables to be assessed for these outcomes include age, gender, current
674 smoking status (at each visit), pack-years, baseline lung function, baseline CT emphysema and
675 airway measures, respiratory symptoms (e.g., chronic bronchitis, dyspnea), respiratory
676 medications, and co-morbid illnesses (including lung cancer and coronary artery disease).
677 Exacerbation frequency will be assessed as a predictor of primary outcome measures.
678 Transformations of CT and spirometric progression measures from among the Box-Cox family
679 of transformations will be considered to stabilize variance estimates across the ranges of CT
680 measurement values. We will compare the demographic and clinical characteristics of subjects
681 who have follow-up data to those subjects missing due to death and those subjects missing due to

682 loss to follow-up. Longitudinal analysis will be performed including time-dependent covariates
 683 such as change in current smoking status. Time-dependent covariates in these analyses include
 684 change in current smoking status and change in pulmonary medications. Disease progression and
 685 mortality will be simultaneously assessed to limit potential bias introduced by differential
 686 survival. This analytical approach considers the joint distribution of the vector of repeated
 687 measures (i.e., longitudinal progression of PFT abnormalities and CT measures) simultaneously
 688 with time to event (i.e., mortality) using the method developed by Hogan and Laird(10).
 689 The power to detect differences in 10-year changes between subtypes of COPDGen subjects
 690 was assessed for FEV₁, PERC15, adjusted lung density, and % gas trapping. These calculations
 691 used the mean and standard deviation (SD) with estimated changes in FEV₁(11), PERC15(12),
 692 adjusted lung density, and % gas trapping based on the 5-year follow-up visits. We assumed a
 693 significance level of 0.05 and equal variance of the change in each subtype group. These
 694 conservative calculations are based on comparing differences in rates of change for COPD-
 695 related phenotypes among two hypothetical groups of subjects ranging in size from 250 to 2000,

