721 level resolution is most reflective of underlying biology, it is technically challenging to
722 accurately infer isoform levels from short-read fragments(17), and for some applications gene or
723 exon-level quantifications may be preferable to isoform quantification(14, 15). Gene-level
724 quantification of differential expression analysis will be performed using voom/limma, which
725 accounts for the distributional aspects of RNA-Seq data through a weighted regression approach.
726 Identification of differential exon usage will be performed using a novel implementation of
727 DEXSeq adapted for large studies. These tools are all implemented in R/Bioconductor. Isoform
728 quantification and differential expression analysis will be performed using pseudoalignment-
729 based methods such as kallisto(18) and sleuth for isoform quantification and differential
730 expression, respectively. Associations of gene expression to COPD subtypes will be adjusted for
731 covariates, including complete blood count differentials. Surrogate variable analysis will be used
732 to correct for potential batch effects and to remove unwanted sources of variability.(19)

733
734 For proteomics analysis, the relationships between the categorical and quantitative outcomes and
735 the predictor variables (~1310 individual plasma protein biomarkers in the SOMAScan panel)
736 are assessed using standard regression models. Covariates in these analyses include age, gender,
737 pack-years of smoking, and current smoking. To control the false discovery rate, the Benjamini-
738 Hochberg method is used to adjust the p-values. These biomarker measurements will be
739 integrated with pQTL genetic variants to improve accuracy of risk prediction.

740
741 COPD-related phenotypes will be assessed with whole genome sequencing (WGS) data for
742 possible associations with both rare and common variants. In addition, for each protein and
743 transcript that shows significant differences among COPD subtypes or between cases and control
744 subjects, both *cis* (within 1 Mb) and *trans* (genome-wide) association analysis will be performed
745 using WGS data. Although we will re-evaluate analytical methods for rare variants when our
746 Omics and WGS data become available, our current primary analysis plan is to test single
747 common and rare variants using linear regression or the Firth test, and the Sequence Kernel

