	20	40	60	80
Odds ratio of 2.25	24.3	43.1	68.2	82.7
Odds ratio of 2.5	32.1	58.8	84.9	95.4

773
 774
 775 We will also perform epidemiological and Omics analysis in 800 subjects from the Short-Term
 776 Follow-Up Study Population. The relationships between the outcomes of interest (FEV₁ and
 777 adjusted lung density) of each of the three high risk groups compared to the reference group will
 778 be assessed using linear mixed models. Covariates in these analyses will include risk group, visit,
 779 age, gender, pack-years of smoking, current smoking status, and baseline FEV₁ % predicted. The
 780 relationship between changes in FEV₁ and changes in adjusted lung density will be assessed by
 781 including time-varying as well as subject mean values in the model as predictors. An
 782 unstructured covariance structure (or other appropriate structure) will be used in the model to
 783 account for repeated measures. We will adjust for multiple statistical testing by requiring
 784 $p < 0.01$ to demonstrate any significant association.

785
 786 The power estimates to detect differences in change in FEV₁ or adjusted lung density for the
 787 Short-Term Follow-Up Study are shown in **Table 4**. Two rapid progression groups will be tested
 788 for change in FEV₁ (High COPD Progression Score and Paraseptal Emphysema) and two rapid
 789 progression groups will be tested for change in adjusted lung density (High Risk Airway Disease
 790 Axis and Paraseptal Emphysema). Based on the five-year changes in those groups compared to
 791 non-high risk subjects, 200 subjects per group will provide excellent power to detect differences
 792 between the rapid progression and non-high risk groups over one year. Power to detect
 793 differences for RNA-Seq and proteomic biomarkers between 200 rapid progression and 200 non-
 794 rapid progression subjects was assessed. We will have 80% power to detect effect sizes > 0.6
 795 standard deviations, which will be adequate to detect useful biomarkers.

796

Outcome	Rapid Progression Group	Sample Size of Each Short-Term Follow-Up Group		
		100	200	300
FEV ₁ , ml/yr	High COPD Progression Score	100	100	100
	Paraseptal Emphysema	72	95	99
Adjusted Lung Density, per yr	High Risk Airway Disease Axis	100	100	100
	Paraseptal Emphysema	100	100	100

797
798
799
800
801
802
803
804
805
806

VIII. RISKS AND DISCOMFORTS

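### Table 4's paraseptal emphysema FEV1 row was not calculated at the p<0.01 the protocol requires; at that level the stated 95% power with 200 per group is about 85%

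*Protocol*

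**What the plan says.** All of this is in the Protocol, section VII (Biostatistical Analysis). The first Short-Term Follow-Up paragraph announces epidemiological and omics analyses in 800 subjects. It then describes linear mixed models comparing FEV1 and adjusted lung density in three high-risk groups with a reference group. It closes with the multiplicity rule: "We will adjust for multiple statistical testing by requiring" "p < 0.01$ to demonstrate any significant association".

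The next paragraph introduces Table 4. "Two rapid progression groups will be tested" for FEV1 and two for adjusted lung density, which makes four comparisons. It says that, relative to "non-high risk subjects, 200 subjects per group will provide excellent power to detect differences" over one year. The row at issue reads "Paraseptal Emphysema 72 95 99", for 100, 200 and 300 per group. The other three rows show 100 in every cell. No significance level is given for Table 4. The only level stated for an epidemiological power calculation is the "significance level of 0.05 and equal variance of the change in each subtype group", which belongs to Table 2.

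On biomarkers, the same paragraph states for 200 against 200 subjects: "We will have 80% power to detect effect sizes" above 0.6 SD, with no level given. The earlier proteomics text has its own rule for about 1,310 proteins: "To control the false discovery rate, the" Benjamini-Hochberg method is used.

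**The concern.** A power figure describes one test at one significance level. Here the decision rule and the power table stand in consecutive paragraphs, so a reader will take Table 4 as the power of the p<0.01 rule. If the table was computed at a looser level, its figures are too high for the test that will be applied.

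The paraseptal FEV1 row is the only one where this can matter, because it is the only one not saturated at 100%. The 200 column is the operative one: three high-risk groups and one reference group in 800 subjects make 200 each. At stake is whether the chance of missing the assumed FEV1 difference is 5% or about three times that.

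**Working it through.** **Inputs.** From Table 4: 72, 95 and 99% at n = 100, 200 and 300 per group. From the mixed-model paragraph: p<0.01, whose sidedness is not stated and which I take as two-sided. The standardised difference d is not given, so I solve for it from the row.

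**Formula.** For two equal groups of n, power = Φ(d·√(n/2) − z₁₋α/₂). I checked the results with the noncentral t.

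**Step 1: reproduce the row.** Take α = 0.05 (z = 1.960) and d = 0.36.

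| n per group | d·√(n/2) | minus 1.960 | power | stated |
|---|---|---|---|---|
| 100 | 2.546 | 0.586 | 72% | 72 |
| 200 | 3.600 | 1.640 | 95% | 95 |
| 300 | 4.409 | 2.449 | 99% | 99 |

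The match is exact after rounding.

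**Step 2: try α = 0.01** (z = 2.576).
- Fixing 72% at n = 100 gives d = (2.576 + 0.583)·√(2/100) = 0.447. The row would then read 72.0, 97.1 and 99.8%.
- Fixing 95% at n = 200 gives d = (2.576 + 1.645)·√(2/200) = 0.422. The row would then read 65.9, 95.0 and 99.5%.

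Neither is the printed row. One-sided 0.01 fails as well: fixed at 72%, it gives 96.3 and 99.7%.

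**Step 3: which levels fit?** Searching over α and d together with the noncentral t, two-sided levels of about 0.034 to 0.070 reproduce all three rounded cells. The level 0.05 is the conventional value inside that range and the one stated for Table 2. The level 0.01 lies well outside it.

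**Step 4: power at the declared level**, d = 0.36, α = 0.01.

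| n per group | d·√(n/2) − 2.576 | power, normal | power, noncentral t |
|---|---|---|---|
| 100 | −0.030 | 48.8% | 47.9% |
| 200 | 1.024 | 84.7% | 84.4% |
| 300 | 1.833 | 96.7% | 96.6% |

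Over all the (α, d) pairs from Step 3, power at 200 per group under p<0.01 runs from about 80 to 89%.

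Size needed for 95%: n = 2·[(2.576 + 1.645)/0.36]² = 2·(11.725)² ≈ 275 per group.

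**Step 5: the other three rows.** A printed 100 at n = 100 means at least 99.5%. Taking 0.05 as the level, d is at least (1.960 + 2.576)·√(2/100) = 0.641. At α = 0.01 that leaves at least 97.5% at n = 100 and more than 99.9% at n = 200.

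**Step 6: the biomarker figure.** For 0.6 SD with 200 per group, d·√(n/2) = 6.0. Power of 80% requires z₁₋α/₂ = 6.0 − 0.842 = 5.158, so two-sided α is about 2.5×10⁻⁷ (4.2×10⁻⁷ by the t distribution). At α = 0.01 the power would be Φ(6.0 − 2.576) = 99.97%. The 0.6 SD statement was therefore not built on p<0.01.

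**The case against.** The strongest reply is that little changes. No level is printed for Table 4, so 0.05 is an inference. Only one row of four moves materially. That row stays at about 85%, above the 80% the protocol itself accepts for biomarkers. The rule is also sound for its likely purpose: with four comparisons Bonferroni gives 0.05/4 = 0.0125, and 0.01 is slightly stricter. All of this stands, and it limits the seriousness of the point. It does not remove the mismatch, because no level near 0.01 reproduces the row.

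Two stronger readings are tempting, and the protocol does not support either.

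A reader might infer that p<0.01 also governs the transcript and protein tests, which would admit many false biomarkers. The paragraph does open with omics, and its rule is worded to cover every association. But after that opening it describes only the FEV1 and lung density models, the proteomics text prescribes Benjamini-Hochberg, and the 0.6 SD figure implies a level near 10⁻⁷ to 10⁻⁶. The fair criticism is ambiguity of scope. Nor is it a fault in itself that a few clinical comparisons and thousands of biomarkers have different thresholds.

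A reader might also infer that one-year power is far lower still, because Table 4 rests on five-year changes, and dividing a five-year SD by five would shrink measurement error that a one-year change keeps in full. The protocol gives neither the SD nor how it was scaled, so any figure would rest on invented inputs.

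**Conclusion.** The point holds for one row and one decision rule. The stated 95% power for the paraseptal emphysema FEV1 comparison at 200 per group is not the power of the stated p<0.01 test, which is about 85%. The chance of missing the assumed difference is about 15% rather than 5%. At 100 and 300 per group the figures become about 48 and 97%.

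This rests on three assumptions: p<0.01 is two-sided; the row came from a two-group comparison of means with a common effect size across the three columns; and the level used was 0.05. Relaxing the last to any level that fits the rounded row gives 80 to 89%. The remaining rows, and the choice of 200 per group, are essentially unaffected. Separately, the reach of p<0.01 over the omics analyses is unclear in the text and should be settled. Overall this is a should-fix correction.

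**What to change.** 1. Recompute Table 4 at two-sided 0.01, print that level with the table, and restate the paraseptal emphysema FEV1 figure at 200 per group as about 85%. The sponsor holds the actual effect and SD and can replace the back-solved value.
2. Add one clause limiting p<0.01 to the mixed-model comparisons of FEV1 and adjusted lung density, and stating that the Benjamini-Hochberg rule from the proteomics text applies to the Short-Term Follow-Up omics analyses.

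The cost is one recalculated table and a sentence or two. No design element or data collection changes; one power figure becomes less favourable.

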72 of death.

73

74 **Specific Aim 3: Rapid Disease Progression Subtypes (Short Term Follow-up Study)**

75 To test high-risk subtypes for rapid COPD progression, approximately 800 subjects from the full
76 COPDGene cohort will participate. These subjects will be invited back for a Short Term Follow
77 up Study visit approximately one year after the Phase 3 visit.

78 Subjects participating in the Short-Term Follow-Up study will be identified by the Data
79 Coordinating Center and a list will be provided to each participating clinical center.

80 III. SUBJECT SELECTION- Phase 3

81 In summary, Phase 3 is the 10-year and 11-year (short-term follow up for applicable subjects)
82 return visit. Phase 3 is also the 5-year return visit for Non-Smokers enrolled in Phase 2.

83

84 All subjects to be studied have been enrolled in the Genetic Epidemiology of COPD Study
85 (COPDGene) in previous phases. As part of their original informed consent for COPDGene and
86 subsequent consent at the 5-year follow-up visit, subjects have provided consent to be re-
87 contacted for periodic follow-up and for other studies.

88 This project will invite all 10,371 subjects who are alive and still in the study who successfully
89 completed a Phase 1 visit for a Phase 3 study visit. At the time of writing this protocol, there are
90 1,573 deceased subjects. All non-smokers enrolled in Phase 2 will also be eligible to return for a
91 visit 5 years (\pm 6 month) after their first visit, in total 349 new non-smokers were enrolled in
92 Phase 2. This is a total of 10,720 subjects in the cohort. Phase 3 will be scheduled 10 years (\pm 6
93 months) after Phase 1 or 5 years (\pm 6 month) after Phase 2 (for new subjects enrolled in Phase 2).
94 There must be at least 3 years in between the Phase 2 and Phase 3 visits. Visits later than the
95 scheduled return visit *are* permitted. The Short-Term Follow-Up Study for rapid progressors
96 will occur approximately one year after the subject participates in the Phase 3 study.

97 A key component of the project is to establish contact with all of the previously enrolled subjects
98 who remain in the study or confirm the subjects are deceased. Clinical centers will utilize locally
99 stored contact information including secondary contacts to establish contact.

100 Eligible subjects will be contacted mail, email and/or phone and invited to participate in Phase 3

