 696 which will be created from the 4500 subjects with follow-up spirometry, clinical measures, and
 697 chest CT scans in Phase 3 (**Table 2**). Using these assumptions, there is adequate power to detect
 698 differences between subtype groups with as few as 250 subjects. By 2-sided log rank test, we
 699 will have virtually 100% power to detect a 15% difference in all-cause or cause-specific
 700 mortality between the slow and fast FEV₁ decline groups in Table 2.
 701

Table 2: Power (%) for Longitudinal Epidemiology Analysis

Outcome	Difference Between Groups over 10 yrs	Sample Size of Each Subtype Group for Pairwise Comparisons			
		250	500	1000	2000
FEV ₁ , ml	100	97	100	100	100
	200	100	100	100	100
PERC15	4	75	96	100	100
	8	100	100	100	100
Adjusted Lung Density	2	46	75	96	100
	4	96	100	100	100
% Gas trapping	2	70	94	100	100
	3	96	100	100	100

702
 703 The primary phenotypes for genetic, transcriptomic, and proteomic analysis will be each COPD
 704 subtype vs. smoking controls; the quantitative emphysema and airway disease axes; and the
 705 change in FEV₁ and adjusted lung density between the 5-year and 10-year visits. In addition, a
 706 number of secondary analyses will be performed, including: a) presence/absence of COPD
 707 (comparing subjects with GOLD 2-4 COPD to smoking controls); b) cross-sectional measures of
 708 CT emphysema, CT gas trapping, CT airway wall area, FEV₁, 6MWD, oxygen saturation,
 709 emphysema distribution, and chronic bronchitis; and c) longitudinal measures of exacerbation
 710 frequency and change in CT gas trapping, CT airway wall area, and 6MWD. Cross-sectional and
 711 longitudinal COPD-related phenotypes will be assessed within each COPD subtype and within
 712 the entire study population. Longitudinal imaging and lung function phenotypes will be assessed
 713 as both change over time (between the 5 and 10-year visits and across all three visits) and
 714 average outcomes over all three visits.
 715

716 Phase 2 blood RNA-Seq will be used to generate gene, exon, and isoform-level estimates of
 717 relative expression abundance. RNA-Seq data will be processed by the CDNM bioinformatics
 718 pipeline that addresses sequencing errors and other technical artifacts. Alignment to the human

719 reference genome will be performed with STAR(13), followed by multiple quantification and
720 analysis options, including DESeq2(14), DEXSeq(15), and voom/limma(16). While isoform-

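### Table 4 claims one-year power from five-year changes without printing its difference, SD or alpha, and its one informative row fits alpha 0.05 although the analysis requires p<0.01

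*Protocol*

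**What the plan says.** Section II, Specific Aim 3 of the Protocol brings about 800 subjects back for a Short Term Follow "up Study visit approximately one year after the Phase 3 visit". The summary table in section IV says that the rapid progressors are identified from the Phase 2 data.

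Section VII plans linear mixed models for FEV1 and adjusted lung density, with visit among the covariates and an unstructured (or other suitable) covariance. It does not say which visits enter. Multiplicity is handled by requiring p<0.01 "to demonstrate any significant association".

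The power statement reads "Based on the five-year changes in those groups compared to" subjects not at high risk, "200 subjects per group will provide excellent power to detect differences" "between the rapid progression and non-high risk groups over one year". Table 4 is on a yearly scale (FEV1 in ml/yr; "Adjusted Lung Density, per yr"). Its FEV1 row for "Paraseptal Emphysema" is 72, 95 and 99% at 100, 200 and 300 per group. The other three rows are 100% throughout. The text gives no group difference, SD or alpha for this table. The stated alpha of 0.05 belongs to the ten-year calculation in Table 2.

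**The concern.** The effects come from a five-year interval and the claim is for a one-year interval. A steady difference in rate of decline shrinks in proportion to the interval. Visit-to-visit error does not: each change score contains the error of two visits, however far apart they are. Dividing a five-year change by five also divides its error SD by five, whereas a measured one-year change carries that error whole. Power computed from an annualised five-year SD is therefore too high for a one-year change.

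Separately, the threshold at which significance will be declared is p<0.01. If the table was computed at 0.05, its power belongs to a test that will not be used.

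This power is what justifies the one-year visit and the 200 per group. If it is overstated, a null result for a rapid-progression group could be read as absence of rapid progression when the comparison had little chance of showing it.

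**Working it through.** All power figures use the two-sided normal approximation for two equal groups: power = Φ(d√(n/2) − z) + Φ(−d√(n/2) − z), where d is the standardised difference, n the number per group, and z = 1.960 (alpha 0.05) or 2.576 (alpha 0.01).

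**1. Reproducing the FEV1 paraseptal row.** With no inputs printed, d has to be back-solved.
- Two-sided alpha 0.05, d = 0.36: 72.1 / 95.0 / 99.3%, against the printed 72 / 95 / 99. All three figures are matched for d between 0.358 and 0.362.
- Two-sided alpha 0.01: no single d fits. Solving at n = 100 (d = 0.447) gives 72.0 / 97.1 / 99.8%. Solving at n = 200 (d = 0.422) gives 65.9 / 95.0 / 99.5%.
- One-sided 0.05 and one-sided 0.01, solved at n = 100, give 72 / 93.4 / 98.7% and 72 / 96.3 / 99.7%. These are close but do not match the printed integers.

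**2. The same effect at the plan's own threshold.** d = 0.36 at p<0.01 gives 48.8 / 84.7 / 96.7% at 100 / 200 / 300 per group.

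**3. The rows at 100%.** A figure that rounds to 100 at n = 100 requires power of at least 99.5%, so d is at least 0.64 (alpha 0.05). Nothing bounds d from above. Even at this minimum, the p<0.01 rule alone leaves about 97% at 100 per group and over 99.9% at 200.

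**4. From five years to one year.** Assumption: d = 0.36 is the five-year standardised difference, which is what annualising preserves. Set the five-year change variance to 1 and let f be the share that is visit-to-visit error. The Protocol does not give f.
- One-year difference = five-year difference / 5.
- One-year variance = f + (1 − f)/25.
- Ratio of one-year SD to annualised SD = √(f + (1 − f)/25) / 0.2.
- One-year d = 0.36 / ratio.

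| f (assumed) | SD ratio | One-year d | Power, n = 200, alpha 0.05 | Power, n = 200, p<0.01 |
|---|---|---|---|---|
| 0 | 1.00 | 0.360 | 95% | 85% |
| 2% | 1.22 | 0.296 | 84% | 65% |
| 5% | 1.48 | 0.243 | 68% | 44% |
| 10% | 1.84 | 0.195 | 50% | 27% |
| 50% | 3.61 | 0.100 | 17% | 6% |

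On this assumption the printed 95% holds only if visit-to-visit error is practically absent from the five-year change.

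**The case against.** **The SD may not have been annualised.** The Protocol nowhere says that an SD was divided by five. The reference to five-year changes may describe only where the effect sizes came from, with a proper one-year SD behind the table. This stands, and it is why step 4 is conditional. Annualising remains the likelier reading, because five-year changes are the only source named and the rows are per year.

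**A reader might infer from Table 2 that Table 4 can be reached only by annualising.** Table 2, headed "Difference Between Groups over 10 yrs", back-solves to an FEV1 SD of about 291 ml and a density SD of about 12.0. Multiplying 0.36 by 291 gives 105 ml in one year, which looks impossible beside 100 to 200 ml over ten years. The documents do not support that argument. It applies an SD of ten-year change to a one-year change, although the slope part of the variance shrinks with the interval. Under the model of step 4 with f = 10%, the ten-year variance is 4 × 0.9 + 0.1 = 3.7 and the one-year variance is 0.136. The one-year FEV1 SD is then 291 × √(0.136/3.7) = 56 ml, and 0.36 SD is about 20 ml, which equals Table 2's upper rate (200 ml over ten years). For density, 0.64 × 12.0 × √(0.136/3.7) is about 1.5 units, still well above Table 2's 0.2 to 0.4 per year. But Table 2 compares hypothetical groups, not groups selected as rapid progressors. Table 2 therefore does not settle how Table 4 was built.

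**The mixed model may use earlier visits.** The text does not restrict it to the last two. For a common slope over years 0, 5, 10 and 11, power at 200 per group would be 98% or more at alpha 0.05 for error shares of 25% and above. With years 5, 10 and 11, the error variance of a subject's least-squares slope falls from 2σ² (two visits one year apart) to σ²/20.67, about 41-fold. The gain is real, but the quantity becomes a multi-year rate and the claim is for one year. Because the groups were identified from Phase 2 data, reusing a Phase 2 measurement that determined selection would also invite regression to the mean.

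**The inputs may be in a separate analysis plan.** They may be, but the power itself is printed here and used to justify the sample size, so its basis should be checkable here.

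**Conclusion.** The point holds in two parts of different strength.

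*Firm.* The only row that carries information fits two-sided alpha 0.05, while the section requires p<0.01. At that threshold the same effect gives about 85% at 200 per group instead of 95%, and 49% instead of 72% at 100. This rests on back-solving the printed integers as a two-group comparison, with no assumption about SDs.

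*Conditional.* If the SD is an annualised five-year SD, the FEV1 paraseptal power for a one-year change at 200 per group is about 84%, 68%, 50% or 17% at alpha 0.05, for assumed error shares of 2%, 5%, 10% or 50%. Both the annualising and the share are assumptions.

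A reader might go further and conclude that the whole 95 to 100% is unattainable, or that the FEV1 comparison as a whole is uninformative. Neither follows. A one-year SD may have been used, and the other FEV1 row (High COPD Progression Score) and both density rows are known only to have d of at least 0.64, so their loss cannot be sized. What can be said is that the printed one-year power is not supported by what is printed with it.

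**What to change.** 1. Recompute Table 4 at p<0.01 with the SD of a one-year change: variance = slope variance over one year + 2 × visit-error variance. Both components can be estimated from existing repeat visits; subjects with three visits allow the two to be separated.
2. Print the assumed difference, SD and alpha for each row, and restate the power and the sentence that relies on it.
3. State which visits enter the mixed model. If earlier visits are added for precision, call the result a multi-year rate. Do not use as an outcome any Phase 2 measurement that determined entry to a rapid-progression group.

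The cost is one table re-run and two or three sentences, with no new data. The price is that stated power will fall for the FEV1 paraseptal row, and possibly for others, if only the one-year change is analysed. If more visits are used, the study answers a question about a longer-run rate, and leaving out selection-defining Phase 2 values gives back some of the precision gained.
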